6.6.1.2 Randomisation visit (up to 16 weeks' 0 days' gestation)

- Masked CGM sensor review (to confirm adequate baseline data available, where possible).
- Collection / confirmation of completed baseline questionnaires
- Record diabetes treatment
- Randomisation via study website
- Participant training

6.6.1.2.1 Participant training – intervention arm

Patients randomised to the CGM arm will receive training (face to face or virtually) in the following:

- How to apply the sensor
- Understanding the FreeStyle Libre 3 apps, including sharing of data and setting alarms
- Interpreting CGM data
- Recommended targets and managing their diabetes in pregnancy (including 'Top Tips' guidance document)
- Metformin/insulin dose adjustment (if relevant)

The local study team will ensure that the participant has the skills and confidence required to proceed with CGM. If women are unable to demonstrate competency and/or compliance, their withdrawal from the study will be considered.

CGM training modules (non-trial specific) are available at https://abcd.care/dtn/diabetes-tech-pregnancy and can be accessed by trial participants and staff.

Participants will be encouraged to use CGM from randomisation until after delivery, with CGM sensor data captured up to maternal hospital discharge (or up to 14 days post-delivery, whichever is

sooner). Where the participant continues to wear intervention sensors following hospital discharge after delivery, data will continue to feed into the study LibreView account. Data post-hospital discharge will not be used in the analysis.

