6.4.6 Treatment discontinuation

In consenting to the trial, participants are consenting to trial interventions, trial follow-up and data collection. However, an individual participant may stop treatment early or be stopped early for any of the following reasons (not exhaustive):

- Unacceptable adverse event
- Any change in the participant's condition that in the clinician's opinion justifies the discontinuation of treatment
- Withdrawal of consent for treatment by the participant
- Significant protocol violation or non-compliance

As participation in the trial is entirely voluntary, the participant may choose to discontinue trial treatment at any time without penalty or loss of benefits to which they would otherwise be entitled. Although not obliged to give a reason for discontinuing their trial treatment, a reasonable effort should be made to establish this reason, whilst remaining fully respectful of the participant's rights.

Participants who discontinue protocol treatment, for any of the above reasons, should remain in the trial for the purpose of follow up, and data collection (including masked CGM sensor data at key timepoints for both intervention and standard care participants), and analysis, if they are willing.

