6.6.1.2.2 Participant training – control arm

Participants randomised to the control arm will receive training (face to face or virtually) in the following:

- Finger-prick SMBG training with a blood glucose meter (as per standard care). Participants will be asked to perform SMBG at least four values daily, including before breakfast (fasting state) and 1 hour after each meal.
- Recommended targets and managing diabetes in pregnancy (including 'Top Tips' guidance document)
- Metformin/insulin dose adjustment (if relevant)

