6.6.5 Early stopping of follow-up

If a participant chooses to discontinue their trial intervention, they should continue to be followed up as closely as possible to the follow-up schedule defined in the protocol, providing they are willing. They should be encouraged and facilitated not to leave the whole trial, even though they no longer use the allocated trial intervention. Should they choose to withdraw from the intervention only, they will be asked if would like to continue to provide outcome data (masked study CGM data / glucose data from other sources, delivery/neonatal/post-partum data and questionnaire data). If, however, the participant decides that they no longer wish to provide further data, we will respect her views and the participant withdrawn entirely from the trial. NCTU should be informed of the level of withdrawal via the study database. Data (and samples) already collected will be kept and included in analyses according to the intention-to-treat principle for all participants who stop follow up early.

The numbers of participants who stop trial follow-up early will be monitored across both arms.

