6.10.4.7 Statistical analysis

A detailed statistical analysis plan (SAP) for the primary and secondary outcomes will be written and approved before database lock and commencement of data analyses. We will report data in line with the Consolidated Standards of Reporting Trials (CONSORT) statement showing attrition rates and loss to follow-up. Analyses will be conducted using the intention-to-treat principle, incorporating data from all participants according to randomised group. Every effort will be made to follow up participants for outcome assessments including those who withdraw from trial interventions.

Descriptive statistics within each randomised group will be presented for baseline values. These will include counts and percentages for binary and categorical variables, and means and standard deviations (SD), or medians with lower and upper quartiles (IQR), for continuous variables, along with minimum and maximum values and counts of missing values. There will be no tests of statistical significance or confidence intervals for differences between randomised groups on baseline variables.

Treatment effects on biomedical outcomes will be estimated using linear mixed models fitted to outcome variables, adjusted for individual baseline where available, and study site as a random factor to account for potential between site differences. Where variables are measured at multiple timepoints, mixed linear models will be used to utilize data at all time points. Treatment effect on the primary neonatal endpoint will be expressed as an odds ratio with 95% CI estimated from a logistic regression model. For the primary maternal endpoint, the comparison between the two treatment arms is based on a general mixed effects regression model. The two primary endpoints will be treated as fixed effects in mixed models.

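### Section 6.6.1.2.1 lets the study team consider withdrawing CGM-arm women from the study after randomisation for poor competency or compliance, against the protocol's own retention and intention-to-treat rules

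*Protocol*

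**What the plan says.** Section 6.6.1.2 lists randomisation and then participant training at the same visit. Section 6.6.1.2.1 opens with "Patients randomised to the CGM arm will receive training (face to face or virtually) in the following", asks the local team to make sure that the woman can manage CGM, and then states: "If women are unable to demonstrate competency and/or compliance, their withdrawal from the study will be considered".

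The parallel control section, 6.6.1.2.2, begins "Participants randomised to the control arm will receive training (face to face or virtually) in the following" and lists only training content. It has no competency or compliance test and no withdrawal provision.

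Other sections treat the same situation differently:
- Section 6.4.6 lists "Significant protocol violation or non-compliance" as a reason for stopping treatment and continues: "Participants who discontinue protocol treatment, for any of the above reasons, should remain in the trial for the purpose of follow up". It names masked sensor data for both arms as part of what is still collected.
- Section 6.6.5 says of women who stop the intervention: "They should be encouraged and facilitated not to leave the whole trial, even though they no longer use the allocated trial intervention". Leaving the trial entirely is described there as the participant's own decision.
- Section 6.10.4.7 states: "Analyses will be conducted using the intention-to-treat principle, incorporating data from all participants according to randomised group". It also promises every effort at outcome assessment in women who withdraw from the intervention.
- Section 8.1 requires the participant to stay in the trial after randomisation for follow-up and analysis as allocated, subject to her freedom to change her mind.

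**The concern.** As written, staff who know the allocation (6.8.2) may consider ending a randomised woman's participation because of how she performs with the device, in one arm only. Two sites could handle the same woman differently: one following 6.6.1.2.1 could withdraw her from the study, and one following 6.4.6 would keep her in follow-up.

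A woman withdrawn entirely at the training stage, by 16+0 weeks, contributes neither a Time-in-Range profile from 20 to 38 weeks nor a neonatal outcome. If women who struggle with the sensor tend to have worse glucose and worse neonatal outcomes, their loss from the CGM arm alone makes that arm look better on both primary outcomes. An intention-to-treat analysis cannot use outcomes that were never collected. The imputation described in 6.10.4.8 is stated for maternal glucose, not for the neonatal composite.

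**Working it through.** **Step 1. The provisions side by side**

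| Question | 6.6.1.2.1 | Rest of the protocol |
|---|---|---|
| What does the woman leave? | The study | The treatment only (6.4.6) |
| Who initiates it? | Staff | For full withdrawal, the participant (6.6.5) |
| Which arm? | CGM only | Both arms (6.4.6, 6.10.4.7, 8.1) |
| Is follow-up continued? | Not if she is withdrawn | Yes, including masked sensors (6.4.6; 6.6 timeline footnote) |

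These cannot all be followed for the same woman. This part needs no assumption.

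**Step 2. Inputs for the size.** From 6.7: control risk of the neonatal composite 48.8%; Time-in-Range SD 20 points; 422 randomised with 10% drop-out, giving 380 analysable or 190 per arm; two-sided 5% level. The primary neonatal outcome is admission or death, so 48.8% applies and not the admission-only 42.2%. The protocol gives neither the share of women withdrawn under this rule nor their outcomes. Both are assumed below, under no true treatment effect.

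**Step 3. Check against the plan's own figure.** The standard error of the Time-in-Range difference is 20 × √(2/190) = 2.05 points. The difference detectable with 90% power is (1.960 + 1.282) × 2.05 = 6.65 points, as stated in 6.7.

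**Step 4. Neonatal composite.** Let a share f of the CGM arm be removed without outcome, with risk p. The risk in those who remain is (0.488 − f·p)/(1 − f), and the control odds are 0.488/0.512 = 0.953.
- f = 2%, p = 60-70%: remaining risk 48.6% to 48.4%, odds ratio 0.99 to 0.98.
- f = 5%, p = 60%: (0.488 − 0.030)/0.95 = 0.482; odds 0.931; odds ratio 0.931/0.953 = 0.98.
- f = 10%, p = 70%: (0.488 − 0.070)/0.90 = 0.464; odds 0.867; odds ratio 0.867/0.953 = 0.91. The spurious risk difference is 2.4 points and the two-sided type I error about 7.3%.

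**Step 5. Time-in-Range, unadjusted complete cases.** If the women removed lie g points below the other women of their arm, the whole-arm mean is f·g below the mean of those who remain. The bias is therefore f·g.

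| Share removed f | Gap g (points) | Bias (points) | Two-sided type I error |
|---|---|---|---|
| 2% | 10 | 0.2 | 5.1% |
| 5% | 10 | 0.5 | 5.7% |
| 10% | 10 | 1.0 | 7.8% |
| 10% | 20 | 2.0 | 16% |

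The type I error is Φ(−1.96 − b/2.05) + 1 − Φ(1.96 − b/2.05), with b the bias. For b = 2.0 this is about 0.16.

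**The case against.** The strongest reply is that one loosely worded sentence stands against several clear ones. It says that withdrawal will be considered and orders nothing. The sentence before it is about being ready to proceed with CGM, so the authors may have meant withdrawal from the intervention. Section 6.6.5 keeps data already collected under intention-to-treat, and masked sensors are already scheduled for women who stop trial CGM. All of this stands, and it limits how often the rule is likely to do harm. It does not settle which text a site should follow, because the sentence names the study.

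Some stronger inferences are not supported:
- *The intention-to-treat comparison is broken.* It is compromised only as far as the rule is used, and the protocol does not say how often that would be.
- *Missing-data methods cannot help.* Section 6.10.4.8 gives multiple imputation from earlier glucose values and a missing-not-at-random sensitivity analysis for women who withdraw, and 6.10.4.1 adjusts for baseline Time-in-Range. The calculation in step 5 ignores both. The gap is for the neonatal outcome, for which 6.10.4.8 states no imputation.
- *Underserved women are removed.* No section links poor competency or compliance with underserved status. That the women removed would have worse outcomes is likewise an assumption.

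The upper scenarios are also demanding. A 10% share would use up the CGM arm's entire drop-out allowance in 6.7. Eligibility already requires willingness to use the devices and 72-96 hours or more of baseline sensor data, which screens out many who would not wear a sensor.

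**Conclusion.** The contradiction is established by the text alone: 6.6.1.2.1 opens a staff-initiated, post-randomisation route out of the study in one arm, and 6.4.6, 6.6.5, 6.10.4.7 and 8.1 do not allow for it.

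The direction of bias, in favour of CGM on both primary outcomes, depends on the women removed having worse outcomes. Its size depends on how often the rule is used. At about 2% removed it is negligible. The range to quote is an odds ratio of about 0.98 to 0.91 for 5-10% removed at 60-70% risk, and 0.2 to 2.0 Time-in-Range points for 2-10% removed with a 10-20 point gap. The 16% type I error needs both extremes at once and no adjustment or imputation. The case for acting rests on the contradiction and the low cost of removing it, not on a demonstrated large bias.

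**What to change.** Reconcile 6.6.1.2.1 with 6.4.6, 6.6.5, 6.10.4.7 and 8.1 by separating device use from study participation:
- State that lack of competency or compliance may bear on whether the woman goes on using the device, which is a clinical matter for her team, but is not a ground for ending follow-up.
- Apply the same retention rule in both arms.
- Continue masked-sensor data at 20, 28, 32 and 36 weeks and neonatal data collection if she is willing, and analyse her as randomised.
- Leave the existing ends of follow-up unchanged, including early pregnancy loss (6.6.1.11) and the participant's own decision to stop providing data (6.6.5).

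The cost is one amended sentence and a clarification to sites. No new procedure is needed, because the footnote to the 6.6 timeline already provides masked sensors for women who stop trial CGM. The amendment should be made promptly, since outcomes not collected in the meantime may not be retrievable.

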6.6.1.2.2 Participant training – control arm

Participants randomised to the control arm will receive training (face to face or virtually) in the following:

- Finger-prick SMBG training with a blood glucose meter (as per standard care). Participants will be asked to perform SMBG at least four values daily, including before breakfast (fasting state) and 1 hour after each meal.
- Recommended targets and managing diabetes in pregnancy (including 'Top Tips' guidance document)
- Metformin/insulin dose adjustment (if relevant)

6.6.1.6 Procedures following training

Following training, participants in the intervention arm will proceed to use CGM throughout pregnancy and delivery. Participants in the control arm will continue to use current methods of glucose monitoring and will keep a paper logbook or electronic diary of their glucose values, which will be reviewed as per routine care. Participants using continuous glucose monitoring will share their sensor glucose data directly with the trial team. Participants in the control arm will have masked study CGM sensors applied at 20, 28, 32 and 36 weeks' gestation to collect comparable outcome data (those using non-study continuous glucose monitoring will be asked to wear a masked study sensor alongside their own to allow comparable data to be collected).

Glucose targets for both groups are as follows:

- fasting glucose levels 3.5-5.3 mmol/L
- 1 hour post-prandial <7.8 mmol/L
- 2 hours post-prandial <6.7 mmol/L
- HbA1c <43 mmol/mol

Treatment should be adjusted by women and local HCP teams using metformin and/or insulin if glucose levels are out of range on three or more occasions and dietary intervention is unlikely to be adequate for optimal maternal glucose levels.

6.6.1.7 Study visits

Follow up visits will be every 4 weeks at ~16/40, 20/40, 24/40, 28/40, 32/40, 36/40 (+/- 2 weeks). It is expected that the majority of ongoing study visits will align with routine NHS antenatal clinic visits however virtual study visits (e.g., using phone or video calls) will be offered if appropriate, and data from community appointments may be used if needed.

At these visits the following data will be recorded on the study database:

- Weight
- Blood pressure
- Glucose monitoring method(s), frequency of glucose testing
- Insulin delivery method(s), dose and type, if relevant
- Other diabetes treatment

• Adverse events of special interest

In addition to the data collected above (6.6.1.7), the following will be performed at key visits:

- Masked CGM for control group participants (14 days data collection) at 20, 28, 32, and 36 weeks' gestation
- Blood collection for HbA1c at 28, 32, and 36 weeks' gestation
- Follow-up questionnaires at 32 weeks' gestation

6.6.1.9 Delivery visit

The following maternal, obstetric and neonatal outcomes will be collected:

- Maternal CGM sensor data
- Mode of delivery (vaginal, instrumental, elective/emergency caesarean section)
- Gestational age at delivery and indication for any preterm delivery <37 weeks
- Infant(s) birth weight
- Adverse events (pregnancy loss <24 weeks, stillbirth, neonatal death)

6.6.1.10 Neonatal follow up

Neonatal assessment is at hospital discharge (or 28 days if admission prolonged). The following data will be collected:

- Neonatal morbidity (treatment for neonatal hypoglycaemia, neonatal jaundice, respiratory distress)
- Neonatal care admission (duration of stay at each level of care: Level 3 intensive care, Level 2 high-dependency care, or Level 1 special care, recorded according to national guidance (BAPM 2010))
- Infant(s) feeding at hospital discharge (exclusive breast feeding/partial breast feeding/exclusive formula feeding)
- Neonatal readmission in the first 7 days after birth (e.g., for neonatal hyperbilirubinemia see section 9, outcome definitions)

6.6.1.11 Early pregnancy loss

In the event of early pregnancy loss, trial follow-up will end (with the exception of follow up of any CGM- or study-related SAEs). Participants on the intervention arm may be asked to return unused devices to the research team.

6.6.3 Blood sampling

HbA1c levels should be measured locally from blood samples.

At baseline (or at any time during pregnancy, if not taken at baseline), a blood sample will be taken and frozen, for later transfer to the Norwich Biorepository for metabolic phenotyping (assessment of maternal baseline pancreatic function: C-peptide and islet cell antibodies). A sample handling Work Instruction will be provided to all sites detailing sample collection and handling procedures. Appropriate tissue transfer agreements will be put in place prior to the transfer of relevant material.

6.6.2 Questionnaires

Participants will be asked to complete the following questionnaires at baseline and again at 32 weeks to assess diabetes distress, glucose monitoring satisfaction, anxiety & depression, and quality of life using short, validated questionnaires targeted as applicable for T2D:

- T2D Distress Scale (DDS)(45)
- Glucose Monitoring Satisfaction Survey (GMSS)(46)
- Patient Health Questionnaire 9-item depression scale (PHQ-9) (47)
- Generalized Anxiety Disorder 7-item scale (GAD-7) (48)
- EQ-5D (49)

These can be completed in participants' own homes electronically or on paper.

The **Type 2 Diabetes Distress Scale (DDS)** consists of 29 items and yields two sets of scores: an 8item core distress score, reflecting overall diabetes-related emotional distress, and a 21-item set of seven source scores, reflecting seven different potential sources of distress. Responses are rated on a 5-point scale from 'not a problem' to 'a very serious problem'.

The **Glucose Monitoring Satisfaction Survey (GMSS)** is a 15-item self-report scale. The T2D version includes 4 subscales: openness, emotional burden, behavioural burden, and worthwhileness.

The Patient Health Questionnaire 9-item depression scale (PHQ-9) reflects the DSM-5 (Diagnostic and Statistical Manual of Mental Disorders) criteria, classifying symptoms on a scale of 0 (not at all) to 3 (nearly every day).

The Generalized Anxiety Disorder 7-item scale (GAD-7) consists of seven questions with response categories of 'not at all', 'several days', 'more than half the days', and 'nearly every day'. Scores are taken as cut-off points for mild, moderate, and severe anxiety.

The EQ-5D Health-Related Quality of Life Questionnaire is a self-rated health status using a visual analogue scale. It provides a self-reported description of current health in 5 dimensions i.e., mobility, self-care, usual activities, pain/discomfort and anxiety/depression. The concept of health in EQ-5D also encompasses both positive aspects (well-being) and negative aspects (illness). The utility score is an expression of the Quality Adjusted Life Years (QALY).

6.6.4 Qualitative interviews

Participants will be purposively sampled by socio-demographic factors to understand how these affect CGM uptake (sensor wear and using CGM data to change diet/medication/insulin doses). To accommodate this breadth of representation, we will invite approximately 20-25 women to take part in the semi-structured interviews. Interviews will usually be scheduled at around 32-36 weeks' gestation, according to the participants convenience, including after birth if preferred. Interpreting will be offered to enable women to participate in other languages.

We will use the NIHR-INCLUDE Framework to achieve representation of underserved women. The topic guides will include themes relating to barriers and facilitators of CGM use, quality of the electronic, written and verbal information given by HCPs, quality of clinical interactions with HCP teams, extent of informal social support from partners, families, and support networks, impact of competing roles and responsibilities, T2D management strategies, stigma of living with overweight/obesity and EOT2D, psychological distress, and perceptions of medicalised pregnancy.

HCP focus group: We will conduct a focus group with HCPs from each NHS site to identify and describe HCP perceptions of the barriers and facilitators of CGM use. It will include topics on the learning from the study training programme, self-reported perception of skills, what they learned from problem solving and good practice sharing sessions and from patients and suggestions for what

further training and support would be needed for HCP teams and women with EOT2D if CGM use were to be rolled out in routine clinical care.

6.6.5 Early stopping of follow-up

If a participant chooses to discontinue their trial intervention, they should continue to be followed up as closely as possible to the follow-up schedule defined in the protocol, providing they are willing. They should be encouraged and facilitated not to leave the whole trial, even though they no longer use the allocated trial intervention. Should they choose to withdraw from the intervention only, they will be asked if would like to continue to provide outcome data (masked study CGM data / glucose data from other sources, delivery/neonatal/post-partum data and questionnaire data). If, however, the participant decides that they no longer wish to provide further data, we will respect her views and the participant withdrawn entirely from the trial. NCTU should be informed of the level of withdrawal via the study database. Data (and samples) already collected will be kept and included in analyses according to the intention-to-treat principle for all participants who stop follow up early.

The numbers of participants who stop trial follow-up early will be monitored across both arms.

